# VERSION HISTORY

SAP Version	Date	Primary Reasons for Amendment				
0.1 (Stable SAP)	14-MAY-2021	N/A				
1.0 (Final SAP)	03-MAY-2022	N/A				

# LIST OF ABBREVIATIONS

Abbreviation	Definition
AE	adverse event
ALT	alanine aminotransferase
aPTT	activated partial thromboplastin time
AST	aspartate aminotransferase
BID	twice daily
BPM	beats per minute
CRF	case report form
DMF	dimethyl fumarate
Gd	gadolinium
HBcAb	hepatitis B core antibody
HBsAb	hepatitis B surface antibody
HIV	human immunodeficiency virus
ICF	informed consent form
ITT	intent-to-treat
IV	intravenous
IVMP	intravenous methylprednisolone
LAR	legally authorized representative
LLN	lower limit of normal

Abbreviation	Definition
MRI	magnetic resonance imaging
MedDRA	Medical Dictionary for Regulatory Affairs
MS	multiple sclerosis
NSAID	nonsteroidal anti-inflammatory drug
PD	pharmacodynamic
PEG	polyethylene glycol
PK	pharmacokinetic
PRO	Patient-reported Outcome
RRMS	relapsing-remitting multiple sclerosis
SAE	serious adverse event
SC	subcutaneous
TTFR	time to first relapse
WHO	World Health Organization

#### 1. Introduction

This SAP is associated with the BLAST study (800MS301) of BIIB917 (Tecfidera) and BG00012 (Plegridy). It is based on version 4 of the study protocol, dated 06-NOV-2020. This is the final SAP for the study and is intended to outline the basic planned analyses at the time of its writing.

The BLAST study was a randomized multicenter double-blind and double-dummy placebocontrolled three arm parallel group study to evaluate the efficacy and safety of BG00012 and BIIB017 in pediatric subjects with Relapsing-Remitting Multiple Sclerosis (RRMS).

#### 2. Study Overview

This was a randomized, multicenter, double-blind, double-dummy, placebo-controlled, 3-arm, parallel-group study to evaluate the efficacy and safety of BG00012 and BIIB017 in pediatric subjects with RRMS.

Unless stated otherwise below, the term *summary statistics* refers to the computation of the mean, standard deviation, median, minimum, and maximum.

# 2.1. Study Objectives and Endpoints

#### **Study Primary Objective**

The primary objective of this study was to evaluate the efficacy of BG00012 and BIIB017, both compared with placebo, in pediatric subjects with RRMS.

# Study Primary Endpoint

The primary endpoint related to this objective was the Time-to-First Relapse (TTFR).

# Study Secondary Objectives

The secondary objectives of this study were as follows:

- To evaluate the safety and tolerability of BG00012 and BIIB017.
- To assess the effect of BG00012 and BIIB017, both compared to placebo, on additional clinical and radiological measures of disease activity.

[figure not shown]
# Study Secondary Safety Endpoints

[figure not shown]
Occurrence of adverse events (AEs) and serious adverse events (SAEs). Number of new or newly enlarging T2 hyperintense lesions on brain MRI scans at Weeks 48 and 96.

Number of Gd-enhancing lesions at Baseline and at Weeks 48 and 96.

Annualized relapse rate at Weeks 48 and 96.

#### Additional Objectives and Endpoints

# 2.2. Study Design

This was a randomized, multicenter, double-blind, and double-dummy placebo-controlled three arm parallel group study to evaluate the efficacy and safety of BG00012 and BIIB017 in pediatric subjects with RRMS.

Approximately 260 subjects aged 10 to 17 years (inclusive) with a diagnosis of RRMS as defined by the revised consensus definition for pediatric MS (Krupp LB, 2013), (Polman CH, 2011) were to be enrolled at approximately 50 sites globally. Eligible subjects were randomized within 6 weeks of screening. At least 25% of subjects were to be no more than 14 years of age. Subjects were stratified by age (10 to ≤ 14 years of age and 15 to 17 years of age) and by site. Subjects were randomized in a 1:2:2 ratio to treatment with placebo, BG00012, BIIB017, respectively. See the Study Activities schedule below for details on study visits. Visits in Week 2 and Week 6 were conducted in-person (optional) or telephonic. Subjects randomized to BG00012 received a starting dose of 120 mg BID orally (twice daily) for 7 days followed by a maintenance dose of 240 mg BID orally. Subjects randomized to BIIB017 were titrated to the target dose of 125 mg: 63 mg on Day 1, 94 mg at Week 2, and 125 mg at Week 4. Once subjects reached the 125 mg target dose, they continued with BIIB017 125 mg subcutaneously (SC) administered every two weeks for the remainder of the study. To ensure blinding across the treatment groups all subjects received BG00012 (or placebo) administered orally BID and BIIB017 (or placebo) administered SC every two weeks.

An Unscheduled Relapse Visit occurred as required to conduct neurological and evaluations within 72 hours of any new neurological symptoms that could indicate the onset of a clinical relapse. Confirmed relapses were treated at the treating neurologist's discretion with intravenous methylprednisolone (IVMP) at any time from Baseline to Week 100. Such treatment did not affect the subject's eligibility to continue in the study. The primary endpoint of the study was the TTFR: therefore, subjects were required to remain on the assigned blinded treatment until they experience their first protocol-defined relapse or disability progression.

During the study, subjects who had a confirmed relapse or disability progression or high lesion burden on MRI at Week 48 (defined as ≥9 new/enlarged T2 lesions) had the option of switching to an alternative therapy in accordance with local practices, or open-label BG00012 (Tecfidera), at the discretion of the Investigator. Subjects discontinued blinded study treatment when they switch to an alternative therapy or open-label BG00012. Subjects who were

switched to an alternative therapy or open-label BG00012 remained in the study to complete the scheduled visits, along with any requisite safety monitoring.

If a subject received open-label BG00012 or an alternative therapy, they were to be assessed at the Open-Label BG00012/Alternative Therapy Visit within 4 weeks of switching.

In addition to clinical monitoring for relapses, efficacy evaluations included assessments of brain MRIs with Gd enhancement at Baseline and Weeks 48 and 96;

[figure not shown]
Baseline and SAEs as well as changes in

Subjects who withdrew were to complete the Early Withdrawal Visit no later than 4 weeks after the last dose of study treatment or alternative therapy.

Subjects whose lymphocyte count decreased to less than the lower limit of normal (LLN) while on study treatment were followed at least every 4 weeks until the lymphocyte count reached LLN. Subjects who completed, temporarily withheld, or permanently discontinued study treatment for any reason and had a lymphocyte count <LLN were to be followed every 4 weeks for 24 weeks, then every 12 weeks (unless clinically indicated more often or at the Investigator's discretion) until the lymphocyte count was at least LLN, or for 48 weeks following treatment discontinuation, whichever occurred sooner, or until the subject was initiated on the appropriate MS treatment, according to local standard of care, following study withdrawal/completion.

See below for a schematic of the study design.

Figure 1: Study Design

#### 2.3. Sample Size Considerations

The primary endpoint of this study was TTFR. In the Phase 3 adult study of BG00012 (Study 109MS301) with the same endpoint, the reduction in the risk of relapse over 2 years while receiving BG00012 240 mg BID compared with placebo was estimated to be 50%. In the Phase 3 adult study of BIIB017 (Study 105MS301) with the same endpoint, the reduction in the risk of

relapse over 1 year (the placebo-controlled period of this trial) while receiving BIIB017 125 µg every 2 weeks compared with placebo was estimated to be 39%. Based on the PARADIGMS study for fingolimod vs. Interferon β-1a (Chitnis, et al., 2018), and consistent with the understanding of pediatric MS, a higher relapse rate was observed in pediatric patients compared to adults. This is supported by internal Biogen Tecfidera trial data on younger adult patients. Based on the proportion of subjects relapsed (61.2%) in the Interferon β-1a arm, and the observed efficacy in DEFINE, CONFIRM (NCT00420212, studies 109MS301 and 109MS302), and PLEGRIDY (NCT00906399, ADVANCE study 105MS301), we conservatively assumed that 75% of subjects in the placebo group would have had their first relapse during the 2-year period. The study would have had at least 80% power to detect a 50% and 39% reduction compared with placebo in the risk of relapse in the BG00012 and BIIB017 arms, respectively, when a total of 153 events (first relapses) were expected to be accrued. The type I error of each comparison was controlled at 0.05. This 3-arm study was to be conducted in a pediatric MS population to evaluate the efficacy and safety of BG00012 and BIIB017, each compared with the same placebo arm. The same goals could have been achieved in 2 separate placebo-controlled studies. However, the 3-arm platform design would allow fewer subjects exposed to placebo. With 2 comparisons to be made separately between different active treatments and placebo (BG00012 vs. placebo and BIIB017 vs. placebo), as in two separate studies, multiplicity adjustment were unnecessary. Taking into the account a 2year discontinuation rate of 15%, the study planned to randomize approximately 260 subjects (approximately 52 subjects randomized to BG00012, 104 subjects randomized to BIIB017, and 104 subjects randomized to placebo). The discontinuation rate was monitored throughout the study, and discontinued subjects were planned to be replaced by new subjects to achieve 80% power.

### 2.4. Study stopping rules

The study protocol allowed Biogen to terminate the study at any time, after informing the Investigators. Biogen was required to notify the Investigators when the study status was changed, including study holds, study completion, and study termination.

# 3. Early termination of study due to sponsor's decision

The BLAST study was put on hold in 2021 due to low recruitment. After notification of all interested parties (investigators, IRBs, ethics committees, and regulatory agencies), BLAST was canceled by Biogen with the consent of the FDA. At the time the study was put on hold, 16 subjects had been screened and 11 subjects had been enrolled.

#### 4. Changes from the protocol-defined statistical analysis plan

Due to the limited number of subjects enrolled and early closure of the study, the data obtained from this study are not sufficient to support the original study objectives and the analyses outlined in the protocol. The protocol statistical analysis plan was adjusted as reflected in this document to summarize the baseline characteristics and safety data. Summary tables of the baseline disease and demographic characteristics will be provided by treatment group; adverse events,

also will be descriptively evaluated: summaries by actual treatment received will be tabulated, with listing provided instead when the data are

limited. Drug efficacy and patient-reported outcome (PRO) data will not be summarized but will be provided in listings.

#### 5. Definitions

**Baseline Value**: the last non-missing observation prior to receiving study treatment on or before Study Day 1.

Enrollment: Subjects will be enrolled in the study on the date the ICF is signed by the subject's

legally authorized representative (LAR).

**Relapse**: A relapse is defined as new or recurrent neurologic symptoms not associated with fever or infection, lasting at least 24 hours, and accompanied by new objective neurological findings upon examination by the examining neurologist. If a subject experiences new neurologic symptoms, the subject (or parent) must contact the treating nurse or physician as soon as possible within 48 hours of the onset of symptoms. An AE should be recorded.

**Study Day**: Study Day 1 is the day of the first dose of study treatment. (It is the Baseline Day in most circumstances. If a necessary measurement is missing on Study Day 1, the baseline value is the last non-missing observation prior to receiving the study treatment on Study Day 1.)

For dates after Study Day 1

Study Day = (Date of assessment) – (Date of Study Day 1) + 1.

For dates prior to Study Day 1

Study Day = (Date of Assessment) - (Date of Study Day 1).

For adverse events

Onset Study Day = (Date of AE or worsening AE) – (Date of Study Day 1) + 1

For Time on Study

Study Duration =  $(End {of Study Date}) - (Date {of Study Day 1}) + 1$ 

#### For Time on Treatment

Treatment Duration = (Date of last dose per CRF) – (Date of Study Day 1) + 1.

[figure not shown]
# Treatment Emergent:

[figure not shown]
A treatment emergent AE is defined as any AE that either occurs or worsens in severity after the first dose of study treatment. If treatment emergence cannot be determined due to incomplete or partial start and/or end dates, the event will be considered treatment emergent.

[figure not shown]
# 5.1. Dates and Points of Reference

Assessment Endpoint(s) Study V	Target Day (Visit 'isit Window)
AE, SAE Safety Continuous enrollment	from N/A

Assessment	Endpoint(s)	Study Visit	Target Day (Visit Window)			
Brain MRI + Gd contrast agent.	Secondary Efficacy	Baseline Week 48 Week 96	Study Day 1 (1-1) Day 337 (330- 344) Day 673 (666- 680)			
Concomitant Medication Monitoring	Safety	Continuous from enrollment.	N/A			
			-			
			-			

## 5.2. Study Treatment

This study was a double-blinded, double-dummy, placebo-controlled trial. To maintain the blind all subjects received a placebo for the treatment they are not assigned.

**BG00012** (Tecfidera) was to be taken orally at a dose of 120 mg BID for the first 7 days (1 capsule daily), and at 240 mg BID thereafter (2 capsules daily). The BG00012 treatment group will receive a placebo injection of BIIB017 vehicle every two weeks.

**BIIB017** (Plegridy) was to be administered SC at a dose of 125 μg every two weeks for 96 weeks. BIIB012 subjects will be titrated to the target dose on the following schedule: 63 μg BIIB017 on Day 1, 94 μg at Week 2, and 125 μg every other week thereafter for the duration of the trial. BIIB017 subjects will receive daily placebo capsule(s) on the same schedule as BG00012 subjects.

**Placebo** subjects were to receive a SC injection of the BIIB017 vehicle every 2 weeks and daily placebo capsules according to the titration regimen for the BG00012 group.

#### 5.3. Study Periods

This is a single period study, with no follow-up period. Screening took place up to 6 weeks prior to Study Day 1. Subjects were enrolled in the study after the informed consent was signed by their LAR.

#### 5.4. Stratification Factors and Subgroup Variables

#### 5.4.1. Stratification Factors

The study was stratified on age and site. Age was the subject age at Baseline (Study Day 1).

- Age
  - Baseline age 10 to less than or equal to 14 years
  - Baseline age greater than 14 years.
- Site—approximately 50 sites will be used world-wide.

Recruitment was used to ensure that at least 25% of subjects were in the 10 to less than or equal to 14 years age group. All analyses that fit a statistical model were to include the age stratification. Analyses were not to be stratified by site.

# 5.4.2. Subgroup Variables

No subgroup analyses are planned for this study.

# 5.5. Analysis Populations

The protocol defines two analysis populations.

#### Safety Population

The Safety population is defined as all subjects who received at least 1 dose of study treatment. Subjects will be analyzed according to the treatment received.

The primary safety analysis of AEs, will be performed on the safety population during the period from the first dose of blinded treatment to the end of blinded treatment.

#### ITT Population

The Intent-to-Treat (ITT) Population is defined as all subjects who are randomized and receive at least 1 dose of study treatment (BG00012, BIIB017, or placebo). Subjects will be analyzed according to the treatment group to which they are randomized.

#### 6. List of Planned Study Analyses

As noted above, BLAST was terminated early due to the severely limited subject enrollment and progress in the study. As a result, the data collected are insufficient to support the original study objectives. The protocol study plan is changed as reflected in this document to briefly summarize the baseline characteristics and safety data by treatment group and overall. The data summaries are descriptive in nature: comparison among the study treatment groups is inappropriate. Drug efficacy and PRO data will not be summarized but will be provided in listings.

#### 6.1. Interim Analysis

No interim analysis was planned for this study.

#### 6.2. Primary Analysis

The primary analysis will be performed after the data base is locked. The primary analysis will consist of two parts: Subject summaries and Safety Analysis. The Subject summaries will provide a complete listing of all collected data for each subject. The Safety Analysis will consist of AE summaries.

# 6.3. Final Analysis

The primary analysis is the final planned analysis. The BLAST study does not envision any long-term follow-up of subjects: the database will be complete at lock following the site close-out visits.

#### 7. Statistical Methods for Planned Analyses

## 7.1. General Principles

The only planned analysis for this study is the final report. This study design is structured to minimize subject exposure to placebo, and because each active arm functions as a distinct study, multiplicity adjustments are unnecessary.

This is a double-blind, double-dummy study. The blind may be broken in case of a medical emergency if the treating physician needs to know the assigned treatment. Once unblinded, the subject will no longer receive study treatment. The investigator must document the cause for the unblinding in the source documents and make efforts to avoid unblinding other study personnel, limiting treatment information to those involved in the medical emergency.

Subjects will be instructed not to take a dose of study drug within 4 hours of a clinic visit to prevent drug-induced symptoms from being observed by study personnel and risk their unblinding. After the final clinical study report is completed, Biogen will inform the clinical investigators who may inform subjects about the treatment they received, if this does not jeopardize ongoing related studies.

Otherwise, all blinding will remain in place until the data base is locked.

Summary statistics for quantitative variables will consist of the mean, standard deviation, number of non-missing observations, minimum, the median, and the maximum. All quantitative data will be summarized with these statistics classified by treatment arm and visit unless otherwise noted below. Summary statistics for categorical data will consist of the frequency count and the percentage with respect to a study-relevant base (usually the number of subjects at-risk).

Among the demographic data, age, baseline height, and baseline weight will be summarized as quantitative variables. Race, ethnicity, sex, and will be summarized as categorical variables. No graphics are planned for the demographic data.

Missing dates will be handled as shown in Table 1 below.

Table 1. Date imputation rules for AE and Concomitant Medication.

	Missing	Condition	Imputed Value			
Start date (AE, concomitant medication)	Day	The event started in the same year and month as Study Day 1 (or treatment period start date)	Study Day 1 (or treatment period start date)			
		Otherwise	01			
	Day and month	The event started in the same year as Study Day 1 (or treatment period start date)	Study Day 1 (or treatment period start date)			
		Otherwise	01JAN			
	Completely mis and year)	No imputation will be performed				
Stop date (AE, concomitant medication)	Day	The event stopped in the same year and month as the End of Study date	The End of Study date or the analysis data cut-off date			
		Otherwise	The last day of the month			
	Day and month	The event stopped in the same year as the End of Study date	The End of Study date or the analysis data cut-off date			
		Otherwise	31DEC			
	Completely mis	ssing (missing day, month,	No imputation will be performed			

For all other situations if date imputation is appropriate the imputation rules are:

If the day is missing, default to the 15th of the month.

If month and day are missing, default to July 1 of the year.

If the year is missing, do not impute a date.

For all historical dates, if the imputation method yields a date after Study Day 1, impute Study Day -2.

All analyses will be programmed in SAS® Version 9.4 or later.

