### OR

Either of the following additional abnormal urine tests at Screening confirmed by a second urinalysis approximately 2 weeks later:

- hematuria, without known etiology
- glycosuria, without known etiology
- 14. Occurrence of an MS relapse within the 30 days prior to randomization (Day 1) and/or the subject has not stabilized from a previous relapse prior to randomization.

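### Three SAP date rules can give wrong or inconsistent values in a few records: a start after a known stop, a last relapse at Day -2, and a pre-dose onset at Day 0

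*SAP*

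**What the plan says.** - **Partial starts (SAP 7.1, Table 1).** With the day missing, Study Day 1 is used if "The event started in the same year and month as Study Day 1 (or treatment period start date". With day and month missing, it is used if "The event started in the same year as Study Day 1 (or treatment period start date". Otherwise the first of the month or 1 January is used. Neither condition mentions the stop date.
- **Other partial dates (SAP 7.1, text after Table 1).** "If the day is missing, default to the 15th of the month". "If month and day are missing, default to July 1 of the year". The fallback is "For all historical dates, if the imputation method yields a date after Study Day 1, impute Study Day -2". These apply where imputation is judged appropriate. They are not bounded by the consent date or by eligibility.
- **Eligibility (Protocol 8.2, exclusion 14).** The criterion excludes "Occurrence of an MS relapse within the 30 days prior to randomization (Day 1").
- **Study day (SAP 5).** The general definition adds 1 for dates after Study Day 1 and nothing for dates before it, so there is no Day 0. The separate adverse event formula begins "Onset Study Day = (Date of AE or worsening AE"), subtracts the date of Study Day 1 and adds 1. It has no pre-dose branch.
- **Where the dates are used.** SAP 7.3 summarises how long before enrollment the last relapse occurred. SAP 7.5 tabulates concomitant medications, and SAP 7.6.1 lists all adverse events. SAP 5 sets enrollment at signature of the consent form, and SAP 5.3 allows up to 6 weeks from screening to Study Day 1.

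**The concern.** These rules are written down, and a programmer will follow them. The question is whether they return values that contradict other information on the same subject, and whether those values reach the outputs that the shortened SAP keeps. They could do so in three places: a medication or SAE record whose start follows its stop, a baseline summary of relapse timing that shows an eligible subject breaching exclusion 14 or relapsing after enrollment, and an adverse event listing numbered differently from every other listing.

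**Working it through.** The plan gives no figure to reproduce. The check applies each rule to worked dates. The example dates are assumptions; the rules are the SAP's.

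**1. Start after a known stop.** Duration = stop - start + 1.
- Study Day 1 is 15 March 2020, start is March 2020 with the day missing, known stop is 10 March 2020. Imputed start is 15 March; duration = 10 - 15 + 1 = -4 days.
- Study Day 1 is 1 June 2020, start is 2020 only, known stop is 1 March 2020. Imputed start is 1 June, 92 days after the stop; duration = -92 + 1 = -91 days.

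The failure is built in: a start set to Study Day 1 is later than any stop before Study Day 1. Over every Study Day 1 in a 365-day year and every earlier stop in the same month, all 5373 of 5373 combinations fail.

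**2. Last relapse at Day -2.** Study Day 1 is 1 June 2020 and the relapse is recorded as 2020. The default is 1 July 2020. That is after Study Day 1, so the fallback gives 30 May 2020, Day -2. The same happens to every year-only relapse in the calendar year of a Study Day 1 before 1 July.

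Frequency, over an assumed uniform grid of 365 Study Day 1 dates and eligible relapses 31 to 365 days earlier (365 × 335 = 122,275 pairs):

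| Missing part | Set to Day -2 | Placed within 30 days of Study Day 1 |
|---|---|---|
| Day and month | 9.3% | 13.5% |
| Day only | 0% | 1.0% |

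The 9.3% can be checked by hand. A Study Day 1 on day k of the year (k = 32 to 181) has k - 31 eligible same-year relapses; 1 + 2 + … + 150 = 11,325, and 11,325 / 122,275 = 9.3%. These are shares of records that already have the date part missing, not of all subjects.

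Interval to enrollment: if consent was x days before Study Day 1, consent date minus imputed relapse date = 2 - x days. This is negative for any x above 2, and is -40 days at the 6-week limit (x = 42).

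Effect on a mean: a true relapse g days before Study Day 1, recorded as 2 days, shifts a mean over n subjects by (2 - g)/n. With n = 4 assumed, g = 60 gives -14.5 days and g = 150 gives -37 days.

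**3. Onset day.** For an event the day before dosing, the adverse event formula gives -1 + 1 = 0, while the general formula gives -1. An event on Day -5 is listed as Day -4. Such events can exist: Protocol 15.3.2 records SAEs from consent.

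**The case against.** The strongest reply is that classification does not depend on these values. SAP 7.5 counts a therapy as concomitant only if it was taken on or after the day of first dose, and SAP 5 defines treatment emergence by occurrence or worsening after first dose. A known pre-dose stop fails both tests whatever start is imputed. Where emergence cannot be determined, SAP 5 deliberately defaults to emergent. That stands. A reader might infer that the SAP as written misclassifies medications and events. The documents support only a risk, which arises if a programmer tests the imputed start alone.

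A medication that ended long before dosing, as in the second example under point 1, may also lie outside the concomitant record, since SAP 5.1 monitors from enrollment. Non-serious adverse events are recorded only from first dose (Protocol 15.3.1), although SAP 5.1 says from enrollment, so the exposed events are mainly pre-dose SAEs.

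The Day -2 case is also uncommon. It needs both day and month missing, and inclusion 6 and exclusion 14 oblige sites to place relapses in time. The SAP's proviso about when imputation is appropriate leaves room not to impute. This makes the case rare; it does not make the stated value right.

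Finally, output is descriptive, SAP 6 rules out comparison between groups, and SAP 6.2 provides a full listing of collected data. This limits the consequence and leaves the rules uncorrected.

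**Conclusion.** The point holds as a minor one: three stated rules return wrong or inconsistent values in identifiable circumstances. They differ in kind. Only a start after a known stop is literally impossible. Day -2 conflicts with exclusion 14 and usually with the enrollment anchor. Day 0 is a numbering inconsistency in SAP 5, not in Table 1, and changes no treatment-emergent status.

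The effect is small and its size is uncertain. Eleven subjects were enrolled and arm sizes are not stated. A 1:2:2 split would imply about 2.2, 4.4 and 4.4. A reader might then argue that one misclassified subject moves an arm percentage by 25 points (1 of 4) to 50 points (1 of 2). That rests on assumed arm sizes, on misclassification that the definitions do not require, and on a single medication or event row, so it should not be quoted as the expected effect. What does follow from the text is an incorrect relapse interval in the SAP 7.3 summary and an onset day off by one in the SAP 7.6.1 listing, if such records exist.

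**What to change.** Make three edits to the SAP.

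1. **Table 1 starts.** Impute to Study Day 1 only if the known or imputed stop is on or after Study Day 1; otherwise use the first of the known month, or 1 January of the known year. Say that a record with no stop date keeps the present rule. The two examples become 1 to 10 March 2020 (10 days) and 1 January to 1 March 2020 (31 + 29 + 1 = 61 days).
2. **Last relapse.** Cap an imputed date at the earlier of Study Day -31 and the consent date. Both bounds are needed: Day -31 satisfies exclusion 14 but can still fall after a consent signed up to 6 weeks before dosing. If the cap falls outside the known year (or the known month, where recorded), leave the date partial and list it only.
3. **Onset day.** For adverse events before Study Day 1, use the SAP's own formula without the added 1, so that the day before dosing is Day -1.

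The cost is a few lines of SAP text and programming. No new data are needed and no clinical procedure changes.
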